### 13.14 Dose Modification

#### 13.14.1 Phase 1

PLX3397 or temozolomide dose reductions and interruptions will be permitted during the 11-week DLT window (Cycle 1 through Cycle 2, i.e., 1 week PLX3397 run-in, 6 weeks of PLX3397 + RT + temozolomide, and 4 weeks of post-RT recovery) only if a patient experiences a DLT (see [Section 13.13.2](#) Dose-Limiting Toxicities). PLX3397 interruptions during the 11-week DLT window are also permitted for Grade 3 vomiting that persists despite optimal supportive care.

If a patient experiences a DLT during the 11-week DLT window, treatment continuation at a lower dose may be permitted at the discretion of the Investigator and in consultation with the Medical Monitor. PLX3397 dose reductions should occur in increments of 200 mg/day, depending on the toxicity grade, as noted in [Table 3](#), PLX3397 Dose Modifications. For dose reductions see [Section 13.13.1](#) Dose Escalation.

If dose interruption continues after the patient's scheduled C3D1 PLX3397 dose administration, the patient should discontinue study treatment and have the procedures outlined in [Section 13.11](#) End of Treatment.

During the adjuvant treatment period, PLX3397 or temozolomide dose reductions and interruptions will be permitted in consultation with the Medical Monitor. PLX3397 dose reductions should occur in increments of 200 mg/day, depending on the toxicity grade, as noted in [Table 3](#) PLX3397 Dose Modifications. For dose reductions see [Section 13.13.1](#) Dose Escalation.

If a patient experiences a DLT, temozolomide dose reduction should be made according to the prescribing information noted in [Attachment 4](#) and also summarized in [Section 16](#).

### 13.14.2 Phase 2

Phase 2 will not include a separate dose escalation design, as there has been no delayed toxicity observed for PLX3397 in extensive nonclinical and clinical evaluations to date, and temozolomide is given at a lower intensity schedule compared to the daily schedule during concomitant radiation therapy. During Phase 2, reduction/interruption of dosing for adverse events may take place at any time during the study according to the guidelines in Table 3.1, Table 3.2, and Table 3.3.

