Dose reduction/interruption guidelines for hematologic and nonhematologic treatment-related TEAEs are based on severity. Dose interruptions can be implemented at the discretion of the treating Investigator to manage intolerable or clinically significant toxicity. If a dose interruption is required, study assessments should be performed as scheduled, irrespective of the study drug delay, with the exception of PK assessments, which should be deferred until treatment is resumed. Interruptions due to toxicity lasting >14 days require treatment discontinuation unless the medical monitor approves continuation.

Dose reductions of temozolomide should be made according to the prescribing information noted in [Attachment 4](#) and also summarized in [Section 16](#).

Below are guidelines for dosage modification for PLX3397-related toxicities as well as guidelines for their management. Dose reductions should occur in increments of 200 mg/day, depending on the toxicity grade, as noted in [Table 3](#), [Table 4](#), and [Table 5](#). As the capsules are provided in 200 mg strengths, dose reduction should occur by a reduction of one capsule from either the morning or evening dose.

Up to 5 days of treatment interruption are permitted for any reason. Interruptions of 6 to 7 treatment days will be considered an acceptable protocol deviation. For interruptions of 8 days or greater, continuation of patients in the study should be discussed with the medical monitor.

Temozolomide dose reduction should be made according to the prescribing information noted in [Attachment 4](#) and also summarized in [Section 16](#).

These parameters are only a guide and are not intended to supersede the clinical judgment of the treating physician. All adjustments should be made in consultation with the Medical Monitor.

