Antiemetic prophylaxis is usually not required for the continuous daily dosing schedule (during radiation). However, prophylaxis with a 5-HT3 antagonist is recommended prior to administration of the first few temozolomide doses and should be administered orally 30 to 60 minutes before temozolomide treatment. Most patients report optimal nausea control with the use of a 5-HT3 antagonist. Routine use of antiemetics is recommended during the adjuvant phase of treatment. Additionally, pneumocystis carinii prophylaxis is at the discretion of the Investigator during the radiation phase.

During the 4-week break after completion of radiotherapy, neither temozolomide nor study drug will be administered.

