## 16.2 Post-Radiation Temozolomide

Patients will receive up to 12 cycles of adjuvant temozolomide at a dose of 150-200 mg/m^2 Days 1-5 of a 28-day cycle and along with PLX3397. Temozolomide will be administered orally once per day for 5 consecutive days (Days 1-5) of a 28-day cycle. The starting dose for the first cycle will be 150 mg/m^2/day, with a single dose escalation to 200 mg/m^2/day in subsequent cycles if no treatment-related adverse events >Grade 2 are noted.

The start of the first cycle will be scheduled 28 days ± 7 days after the last day of radiotherapy. The start of all subsequent cycles (2-12) will be scheduled every 4 weeks (28 days ± 7 days) after the first daily dose of temozolomide of the preceding cycle.

The dose will be determined using the BSA calculated at the beginning of each treatment cycle. The BSA will be calculated from the height obtained at the pretreatment visit and from the weight obtained at the visit immediately before each cycle. Capsules of temozolomide are available in 5, 20, 100, 140, 180, and 250 mg. The daily dose will be rounded to the nearest 5 mg. If the investigator does not want to prescribe the temozolomide 5 mg unit strength, he/she should round off the dose to the closest 10 mg. For example for a 1.7 m^2 subject, the 75 mg/m^2 dose would be 127.5 mg and the dose would be rounded off to 120 mg. For the same subject, the 150 mg/m^2 dose would be 255 mg and the dose would be rounded off to 260 mg. The exact dose administered should be recorded in the CRF. Each daily dose should be given with the least number of capsules.

Patients will be instructed to fast at least 2 hours before and 1 hour after temozolomide administration. Water is allowed during the fast period. Patients will be instructed to swallow the capsules whole, in rapid succession, without chewing them. Treatment should be given at night.

If vomiting occurs during the course of treatment, no re-dosing of the patient is allowed before the next scheduled dose.

Antiemetic prophylaxis with a 5-HT3 antagonist is strongly recommended and should be administered 30 to 60 minutes before temozolomide administration.

Dose reductions of temozolomide during the adjuvant period should be made according to the prescribing information, as summarized below.

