### WARNINGS AND PRECAUTIONS

- Myelosuppression — monitor Absolute Neutrophil Count (ANC) and platelet count prior to dosing and throughout treatment. Geriatric patients and women have a higher risk of developing myelosuppression. (5.1)
- Cases of myelodysplastic syndrome and secondary malignancies, including myeloid leukemia, have been observed. (5.2)

- Pneumocystis carinii* pneumonia (PCP) – prophylaxis required for all patients receiving concomitant TEMODAR and radiotherapy for the 42-day regimen for the treatment of newly diagnosed glioblastoma multiforme. (5.3)
- All patients, particularly those receiving steroids, should be observed closely for the development of lymphopenia and PCP. (5.4)
- Complete blood counts should be obtained throughout the treatment course as specified. (5.4)
- Fetal harm can occur when administered to a pregnant woman. Women should be advised to avoid becoming pregnant when receiving TEMODAR. (5.5)
- As bioequivalence has been established only when given over 90 minutes, infusion over a shorter or longer period of time may result in suboptimal dosing; the possibility of an increase in infusion-related adverse reactions cannot be ruled out. (5.6)

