### 2 DOSAGE AND ADMINISTRATION

#### 2.1 Recommended Dosing and Dose Modification Guidelines

The recommended dose for TEMODAR as an intravenous infusion over 90 minutes is the same as the dose for the oral capsule formulation. Bioequivalence has been established only when TEMODAR for Injection was given over 90 minutes [see *Clinical Pharmacology* (12.3)]. Dosage of TEMODAR must be adjusted according to nadir neutrophil and platelet counts in the previous cycle and the neutrophil and platelet counts at the time of initiating the next cycle. For TEMODAR dosage calculations based on body surface area (BSA) see **Table 5**. For suggested capsule combinations on a daily dose see **Table 6**.

**Patients with Newly Diagnosed High Grade Glioma: Concomitant Phase:** TEMODAR is administered at 75 mg/m^2 daily for 42 days concomitant with focal radiotherapy (60 Gy administered in 30 fractions) followed by maintenance TEMODAR for 6 cycles. Focal RT includes the tumor bed or resection site with a 2- to 3-cm margin. No dose reductions are recommended during the concomitant phase; however, dose interruptions or discontinuation may occur based on toxicity. The TEMODAR dose should be continued throughout the 42-day concomitant period up to 49 days if all of the following conditions are met: absolute neutrophil count greater than or equal to 1.5 x 10^9/L, platelet count greater than or equal to 100 x 10^9/L, common toxicity criteria (CTC) nonhematological toxicity less than or equal to Grade 1 (except for alopecia, nausea, and vomiting). During treatment a complete blood count should be obtained weekly. Temozolomide dosing should be interrupted or discontinued during concomitant phase according to the hematological and nonhematological toxicity criteria as noted in **Table 1**. *Pneumocystis carinii* pneumonia (PCP) prophylaxis is required during the concomitant administration of TEMODAR and radiotherapy, and should be continued in patients who develop lymphocytopenia until recovery from lymphocytopenia (CTC Grade less than or equal to 1).

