#### 5.3 *Pneumocystis carinii* Pneumonia

For treatment of newly diagnosed glioblastoma multiforme: Prophylaxis against *Pneumocystis carinii* pneumonia (PCP) is required for all patients receiving concomitant TEMODAR and radiotherapy for the 42-day regimen.

There may be a higher occurrence of PCP when temozolomide is administered during a longer dosing regimen. However, all patients receiving temozolomide, particularly patients receiving steroids, should be observed closely for the development of PCP regardless of the regimen.

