## 6.2 Postmarketing Experience

The following adverse reactions have been identified during postapproval use of TEMODAR. Because these reactions are reported voluntarily from a population of uncertain size, it is not always possible to reliably estimate their frequency or establish a causal relationship to the drug exposure.

TEMODAR Capsules: allergic reactions, including anaphylaxis, have been reported. Erythema multiforme has been reported, which resolved after discontinuation of TEMODAR and, in some cases, recurred upon rechallenge. Cases of toxic epidermal necrolysis and Stevens-Johnson syndrome have been reported.

There have been reported cases of hepatotoxicity, including elevations of liver enzymes, hyperbilirubinemia, cholestasis, and hepatitis.

Opportunistic infections including *Pneumocystis carinii* pneumonia (PCP) have also been reported. Cases of interstitial pneumonitis/pneumonitis, alveolitis, and pulmonary fibrosis have been reported. Prolonged pancytopenia, which may result in aplastic anemia, has been reported, and in some cases has resulted in a fatal outcome.

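### Section 16.1 leaves Pneumocystis prophylaxis during radiation to the investigator, while the temozolomide label attached to the protocol requires it for every patient on the same regimen; no reason is given

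*Combined protocol and SAP*

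**What the plan says.** Section 16.1 governs temozolomide during radiation. Its antiemetic paragraph ends with the statement that "pneumocystis carinii prophylaxis is at the discretion of the Investigator during the radiation phase". This is the only mention of Pneumocystis in the body of the protocol. It says nothing about when prophylaxis, once started, should stop.

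Attachment 4 reproduces the temozolomide label, which addresses the question in three places:

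- Highlights, Warnings and Precautions: "prophylaxis required for all patients receiving concomitant TEMODAR and radiotherapy for the 42-day regimen for the treatment of newly diagnosed glioblastoma multiforme".
- Label section 2.1: "prophylaxis is required during the concomitant administration of TEMODAR and radiotherapy, and should be continued in patients who develop lymphocytopenia until recovery", with recovery defined as Grade 1 or less.
- Label section 5.3: prophylaxis "is required for all patients receiving concomitant TEMODAR and radiotherapy for the 42-day regimen".

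Label section 14.1 adds that in the newly diagnosed glioblastoma trial prophylaxis was mandatory during combined treatment whatever the lymphocyte count.

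**The concern.** The protocol presents temozolomide with radiotherapy as standard of care and attaches the label for it. On this one safety measure the body is weaker than the attachment, and it does not say why. Section 16.1 leaves open whether to give prophylaxis at all, not merely which drug to use.

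What is at stake is patient safety during combined treatment. Label section 6.2 includes Pneumocystis among the opportunistic infections seen after approval ("pneumonia (PCP) have also been reported"). A site working from section 16.1 would be fully compliant if it omitted prophylaxis. The harm is confined to patients for whom it is omitted, since an investigator who treats everyone satisfies both texts.

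**Working it through.** There is no sample-size or error-rate figure to reproduce. The check compares the texts.

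**1. Is the regimen the same?** The protocol inputs come from the synopsis (Dosage and Regimen) and sections 15.1 and 16.1; the label inputs come from label section 2.1.

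| Item | Protocol | Label |
|---|---|---|
| Disease | Newly diagnosed glioblastoma | Newly diagnosed glioblastoma |
| Temozolomide dose | 75 mg/m² daily | 75 mg/m² daily |
| Duration | About 6 weeks: 6 × 7 = 42 days | 42 days |
| Maximum duration | 49 days | 49 days |
| Radiation | 30 fractions × 2 Gy = 60 Gy | 60 Gy in 30 fractions |

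The rows agree, so a different dose or a shorter course cannot account for the weaker rule.

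**2. Is prophylaxis to be given?** Section 16.1 leaves this to the investigator. The label highlights and label sections 2.1 and 5.3 say yes. The two rules conflict.

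**3. When does it stop?** The label continues it in patients with lymphocytopenia until recovery to Grade 1 or less. Section 16.1 has no rule.

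**4. Does the body import the label's rule by another route?** It uses the label in several places:

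- Section 13.14.1: "If a patient experiences a DLT, temozolomide dose reduction should be made according to the prescribing information noted in" Attachment 4.
- Section 13.14.2: "Dose reductions of temozolomide should be made according to the prescribing information noted in" Attachment 4.
- Section 16.2: "Dose reductions of temozolomide during the adjuvant period should be made according to the prescribing information, as summarized below".
- Section 16.3 says where the full label is and that it highlights key features.
- Section 16.3.6 sends the reader to the label for more on hepatic toxicity.

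The first three concern dose reduction, the fourth is a locator, and the fifth is a pointer on liver effects. None reaches prophylaxis. The adverse-event list in section 16.3.6 does not mention Pneumocystis or opportunistic infection, so the summary does not alert a site to the label's requirement either.

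**5. Does anything in the plan justify a weaker rule?** No reason appears in section 16 or in section 12.0 (Concomitant Treatment). The plan does anticipate low lymphocyte counts: section 13.13.2 excludes Grade 3-4 lymphopenia from the dose-limiting toxicities. The label asks for close watch for Pneumocystis, particularly in patients on steroids, and the response criteria in Attachment 3 expect steroid use. These points give no support to relaxing the rule.

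**6. What cannot be derived.** The documents do not state how many patients would go without prophylaxis, and they give no infection rate with or without it. No expected number of infections can be calculated.

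**The case against.** The strongest case on the other side is practical. Section 16.1 neither forbids nor discourages prophylaxis. Temozolomide is commercially supplied standard treatment, every investigator has the full label inside the protocol, and section 12.0 permits concomitant drugs. From 01 October 2017 visits and laboratory tests move to about every 12 weeks (section 13.10), which suggests that few patients were still to begin radiation. This stands as a limit on the consequence. It does not remove the conflict, and section 13.10 does not state enrolment status; this version still carries the full screening and radiation procedures.

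A second objection is that mandating another drug has its own cost. That also stands. Label section 5.1 notes that sulfamethoxazole/trimethoprim can complicate the assessment of marrow suppression, and the hematologic dose-limiting toxicities in section 13.13.2 carry no relatedness condition. Section 13.13.3 warns that PLX3397 taken with other drugs that affect the liver may raise the risk of severe liver injury. Whether any given prophylactic agent adds to that risk is not in the documents. These are reasons to choose the agent with care and to allow exceptions. The protocol does not offer them as reasons for making prophylaxis optional.

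Three stronger readings are tempting, and the documents support none of them:

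- A reader might infer that patients in fact went unprotected. Discretion is not omission, and no usage data are given.
- A reader might infer that the body relies on the label for dose reductions alone. The hepatic pointer in section 16.3.6 shows otherwise, although it has no bearing on prophylaxis.
- Because PLX3397 acts on macrophage and related cells, a reader might infer that it raises the risk of Pneumocystis. The documents do not say so.

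**Conclusion.** The conflict holds on the text: discretionary in section 16.1, mandatory in three places in Attachment 4, on an identical concomitant regimen, with no stated reason and no rule for continuing prophylaxis in lymphocytopenia. Confidence in that textual finding is high.

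The consequence is much less certain. The period at issue is the 42 to 49 days of combined treatment plus any lymphocytopenia that follows. Neither the number of patients affected nor the harm to them can be quantified, and few patients may still be due to start radiation under this version, an inference from section 13.10. Sample size, power and type I error are unaffected. This is a safety correction worth making because it takes one sentence; it is not a threat to the trial's conclusions.

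**What to change.** Replace the sentence in section 16.1 with wording such as:

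*All patients receive Pneumocystis prophylaxis while temozolomide is given with radiotherapy. In patients who develop lymphocytopenia it continues until recovery to Grade 1 or less. The investigator chooses the agent, taking account of marrow and liver effects (see 13.13.3), and records it as a concomitant medication. If no agent can be given, the reason is documented and discussed with the Medical Monitor.*

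If the sponsor prefers discretion, section 16.1 should state why it departs from the label.

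The cost is one sentence, but by amendment, with the review and approval that section 26.0 requires. Section 12.0 already has concomitant drugs recorded with reason, dose and date. Differential counts to guide stopping are already requested at the end of radiation, in the first week of recovery and at the start of adjuvant treatment (sections 13.6 and 13.7).

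The downsides should be acknowledged:

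- An added drug within the Phase 1b dose-limiting toxicity window may complicate attribution of marrow suppression.
- It may matter for liver toxicity, given the co-medication warning in section 13.13.3.
- It may run into the adjuvant cycles if lymphocytopenia persists. As an indication only, label Table 9 reports Grade 3-4 lymphopenia in 83 of 152 patients (83/152 = 55%), but in anaplastic astrocytoma and on a different temozolomide schedule.

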## 16.2 Post-Radiation Temozolomide

Patients will receive up to 12 cycles of adjuvant temozolomide at a dose of 150-200 mg/m^2 Days 1-5 of a 28-day cycle and along with PLX3397. Temozolomide will be administered orally once per day for 5 consecutive days (Days 1-5) of a 28-day cycle. The starting dose for the first cycle will be 150 mg/m^2/day, with a single dose escalation to 200 mg/m^2/day in subsequent cycles if no treatment-related adverse events >Grade 2 are noted.

The start of the first cycle will be scheduled 28 days ± 7 days after the last day of radiotherapy. The start of all subsequent cycles (2-12) will be scheduled every 4 weeks (28 days ± 7 days) after the first daily dose of temozolomide of the preceding cycle.

The dose will be determined using the BSA calculated at the beginning of each treatment cycle. The BSA will be calculated from the height obtained at the pretreatment visit and from the weight obtained at the visit immediately before each cycle. Capsules of temozolomide are available in 5, 20, 100, 140, 180, and 250 mg. The daily dose will be rounded to the nearest 5 mg. If the investigator does not want to prescribe the temozolomide 5 mg unit strength, he/she should round off the dose to the closest 10 mg. For example for a 1.7 m^2 subject, the 75 mg/m^2 dose would be 127.5 mg and the dose would be rounded off to 120 mg. For the same subject, the 150 mg/m^2 dose would be 255 mg and the dose would be rounded off to 260 mg. The exact dose administered should be recorded in the CRF. Each daily dose should be given with the least number of capsules.

Patients will be instructed to fast at least 2 hours before and 1 hour after temozolomide administration. Water is allowed during the fast period. Patients will be instructed to swallow the capsules whole, in rapid succession, without chewing them. Treatment should be given at night.

If vomiting occurs during the course of treatment, no re-dosing of the patient is allowed before the next scheduled dose.

Antiemetic prophylaxis with a 5-HT3 antagonist is strongly recommended and should be administered 30 to 60 minutes before temozolomide administration.

Dose reductions of temozolomide during the adjuvant period should be made according to the prescribing information, as summarized below.

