--	--

	
12. Women of child-bearing potential who are pregnant or breast feeding.
 
13. At Screening QTcF <math>\geq 450</math> msec for males and <math>\geq 470</math> msec for females.

Dosage and Regimen	
Study drug will be administered orally using a capsule formulation (200 mg per capsule). The total daily dose of PLX3397 will be divided and administered BID. For an uneven number of capsules, the larger dose will be administered in the morning.
 
For Phase 1b PLX3397 dose and schedule cohorts and escalation, see Study Design (above).
 
The Phase 2 portion of the study will use the RP2D selected from the Phase 1b portion of the study.
 
As a part of standard of care, patients will receive the following:
 
 
• 60 Gy of radiation therapy Monday-Friday for a total of 30 radiation treatments over approximately 6 weeks.
 
• Temozolomide 75 mg/m^2 PO once daily for approximately 6 weeks beginning the first day of RT until RT end, followed by adjuvant treatment at a dose of 150 mg/m^2 once daily on Days 1-5 of the first 28 day cycle after completion of radiation therapy (start of Cycle 3). The dose can be escalated to 200 mg/m^2 if the non-hematologic toxicity is Grade <math>\leq 2</math> (except for alopecia, nausea, and vomiting), absolute neutrophil count (ANC) is <math>\geq 1.5 \times 10^9/L</math>, and the platelet count is <math>\geq 100 \times 10^9/L</math>.
 
• During the 4-week break after the completion of RT, neither temozolamide nor study drug will be administered.
 

Safety and Tolerability Assessments	
Physical examinations, vital signs, 12-lead ECGs, adverse events, hematology, and serum chemistry will be used to assess safety and tolerability.
 
As this is an open label study, ongoing safety will be continuously and rigorously monitored by the Sponsor. Additionally, biweekly teleconferences are planned to review in detail the safety across all study sites. Prior to dose escalation in the Phase 1b portion, safety data will be collated and reviewed by the Sponsor and study sites by teleconference.

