### 16.3 Temozolomide Prescribing Information

Full temozolomide prescribing information is located in [Attachment 4](#). Key features are highlighted below.

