#### Maintenance Phase:

**Cycle 1:** Four weeks after completing the TEMODAR+RT phase, TEMODAR is administered for an additional 6 cycles of maintenance treatment. Dosage in Cycle 1 (maintenance) is 150 mg/m^2 once daily for 5 days followed by 23 days without treatment.

**Cycles 2-6:** At the start of Cycle 2, the dose can be escalated to 200 mg/m^2, if the CTC nonhematologic toxicity for Cycle 1 is Grade less than or equal to 2 (except for alopecia, nausea, and vomiting), absolute neutrophil count (ANC) is greater than or equal to 1.5 x 10^9/L, and the platelet count is greater than or equal to 100 x 10^9/L. The dose remains at 200 mg/m^2 per day for the first 5 days of each subsequent cycle except if toxicity occurs. If the dose was not escalated at Cycle 2, escalation should not be done in subsequent cycles.

**Dose Reduction or Discontinuation During Maintenance:** Dose reductions during the maintenance phase should be applied according to **Tables 2** and **3**.

During treatment, a complete blood count should be obtained on Day 22 (21 days after the first dose of TEMODAR) or within 48 hours of that day, and weekly until the ANC is above 1.5 x 10^9/L (1500/μL) and the platelet count exceeds 100 x 10^9/L (100,000/μL). The next cycle of TEMODAR should not be started until the ANC and platelet count exceed these levels. Dose reductions during the next cycle should be based on the lowest blood counts and worst nonhematologic toxicity during the previous cycle. Dose reductions or discontinuations during the maintenance phase should be applied according to **Tables 2** and **3**.

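### Section 16.2 and the synopsis set different conditions for raising adjuvant temozolomide to 200 mg/m²: Section 16.2 has no numeric blood-count threshold and no exempted events

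*Combined protocol and SAP*

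**What the plan says.** Three current texts state when adjuvant temozolomide may go from 150 to 200 mg/m² per day.

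- **Section 16.2:** one step up, in later cycles, "if no treatment-related adverse events >Grade 2 are noted". Subsequent cycles are scheduled by calendar, with no count condition.
- **Section 6.0, Dosage and Regimen:** non-hematologic toxicity must be Grade 2 or lower, continuing "except for alopecia, nausea, and vomiting), absolute neutrophil count (ANC) is" at or above 1.5 × 10⁹/L, with platelets at or above 100 × 10⁹/L.
- **Attachment 4, label section 2.1, Maintenance Phase:** escalation at Cycle 2 "if the CTC nonhematologic toxicity for Cycle 1 is Grade less than or equal to 2 (except for alopecia, nausea, and vomiting", with the same two count limits. It adds "If the dose was not escalated at Cycle 2, escalation should not be done in subsequent cycles" and, for starting any cycle, "The next cycle of TEMODAR should not be started until the ANC and platelet count exceed these levels".

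Table 7, within Section 16.2, links the 200 mg/m² level to Cycles 2 to 6 and to the patient being free of toxicity, without defining toxicity. Table 8 reduces the dose at ANC below 1.0 or platelets below 50 × 10⁹/L, and exempts alopecia, nausea and vomiting from its non-hematologic criteria.

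Section 16.2 invokes the label this way: "Dose reductions of temozolomide during the adjuvant period should be made according to the prescribing information". Section 13.14.2 is similar: "Dose reductions of temozolomide should be made according to the prescribing information noted in" Attachment 4. Section 16.3 has a general pointer: "Full temozolomide prescribing information is located in" Attachment 4. No text says which rule prevails if they differ.

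**The concern.** A site working from Section 16.2 and a site working from the synopsis can make opposite dosing decisions for the same patient. In one direction, a patient with marginal counts receives a higher dose of a myelosuppressive drug than the synopsis intends. In the other, a patient is held at 150 mg/m² when the synopsis would allow 200.

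The trial is uncontrolled and has to judge the safety of PLX3397 combined with temozolomide, so the background dose should not depend on which page a site follows. In Phase 1b, the adjuvant observation period for dose-limiting toxicity covers two cycles (Section 13.13.1). The second of these is the first cycle in which the step can occur.

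**Working it through.** The plan gives no figure to reproduce here. The check is to apply each rule to the same patient.

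**Inputs.** Escalation conditions: Section 16.2, the synopsis and Attachment 4. Reduction limits: Table 8. Platelet boundary for Grade 3: the hematologic DLT list in Section 13.13.2, which prints 50 per µL and is read here as 50 × 10⁹/L. The documents do not define Grade 3 neutropenia; it is assumed to begin at ANC below 1.0 × 10⁹/L.

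| Patient after adjuvant Cycle 1 | Section 16.2 sentence | Synopsis and label criteria |
|---|---|---|
| ANC about 1.0 to <1.5, no related event above Grade 2 | permits 200 | bars 200 |
| Platelets about 50 to <100, no related event above Grade 2 | permits 200 | bars 200 |
| Related Grade 3 nausea or vomiting, no other toxicity above Grade 2, counts adequate | bars 200 | permits 200 |
| ANC <1.0 or platelets <50 | not at issue: Table 8 reduces the dose | bars 200 |

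**Sensitivity to the ANC assumption.** If Grade 3 neutropenia began at some value c, the diverging range would run from the larger of 1.0 (the Table 8 limit) and c up to 1.5. It is non-empty for any c below 1.5, so the assumption sets the width of the range but not whether it exists.

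**An adverse-event test is not a count test.** Section 23.1 asks for a laboratory abnormality to be recorded as an adverse event when it is symptomatic or leads to a change in study or concomitant treatment. A symptomless platelet count of 70 × 10⁹/L might never be recorded as an event.

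**Size of the step.**
- Ratio: 200 / 150 = 1.33, so +33%.
- Per cycle: 5 × 150 = 750 mg/m²; 5 × 200 = 1000 mg/m²; difference 250 mg/m².

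**Duration of the difference.** The synopsis does not confine escalation to Cycle 2. A patient barred at adjuvant Cycle 2 whose counts recover could be escalated at Cycle 3 under the synopsis. The difference between the two rules can then be one cycle, or 250 mg/m².

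**Frequency.** The documents do not give the share of patients in the count ranges. For the third row, the label's glioblastoma trial reports Grade 3 or higher nausea in 3/224 (1.3%) and vomiting in 4/224 (1.8%) over the whole maintenance phase. That was on temozolomide without PLX3397.

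**The case against.** The strongest reply is that a site reading Section 16.2 with its table and the attached label would seldom go wrong on counts. Table 7 reserves 200 mg/m² for patients free of toxicity, and an ANC of 1.2 does not obviously qualify. The label says a cycle should wait until ANC and platelets exceed 1.5 and 100 × 10⁹/L (label section 2.1), and its section 5.1 requires counts at or above those limits before dosing. Section 16.3 points to the full label without limiting its use. A site that applies those rules removes the first conflict.

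This stands as mitigation. It is therefore too strong to infer that Section 16.2 escalates on adverse-event grade alone, because Table 7 adds a restriction, though one with no numbers. It does not remove the conflict: Section 16.2 invokes the label only for reductions, carries no start-of-cycle count rule, and says nothing of the exempted events. The label's count rules do not touch the nausea and vomiting case.

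A second reply is that the synopsis is permissive, so a site escalating only when both rules are met breaches neither. That is true, but no text tells sites to combine them, and doing so withholds a step the synopsis allows. Table 8 exempts the same three events from reduction, which suggests their absence from the escalation sentence is an oversight.

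Two larger figures are tempting and unsupported. One is 11 × 250 = 2750 mg/m² over adjuvant Cycles 2 to 12, or 11,750 against 9,000 mg/m² (+31%). It assumes the comparison patient never escalates, although the synopsis permits later escalation, and that no Table 8 reduction follows in a patient who began with marginal counts. The other scales the label rates to 44 patients: 4/224 to 7/224 gives 0.8 to 1.4. That applies whole-maintenance rates to a decision that may depend on one cycle, and to every patient whether or not adjuvant treatment starts.

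**Conclusion.** The inconsistency is in the current text and should be corrected. Section 16.2 and the synopsis give opposite decisions for ANC of about 1.0 to below 1.5 or platelets of about 50 to below 100 × 10⁹/L, and for related Grade 3 nausea or vomiting. The first direction raises exposure in patients with marginal counts; the second errs toward lower exposure.

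The step is 33%, or 250 mg/m² per cycle, and the excess over the synopsis rule may be as little as one cycle. The exact count ranges rest on the assumed ANC boundary for Grade 3 and on reading the Section 13.13.2 platelet figure as × 10⁹/L. The number of patients affected cannot be estimated.

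A reader might infer that Phase 1b toxicity counts or the recommended dose are distorted. The timing makes that possible, but nothing in the documents allows it to be shown or sized. This is a modest dosing-safety and consistency correction, with no effect on sample size or power.

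**What to change.** Replace the condition in Section 16.2 with the synopsis criteria: escalate to 200 mg/m² only if non-hematologic toxicity was Grade 2 or lower (alopecia, nausea and vomiting exempted), ANC is at least 1.5 × 10⁹/L and platelets are at least 100 × 10⁹/L. State that the most recent count before the escalated cycle governs. For adjuvant Cycle 2 (study Cycle 4) this is the C3D22 count, repeated if below threshold.

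The cost is one condition and one clarifying sentence. Section 13.8 already schedules hematology at C3D22, so no routine visit is added; a repeat is needed only when the count is low.

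Three further edits are optional alignment and not part of the error:
- Limit escalation to adjuvant Cycle 2, as the label does.
- Add the label's start-of-cycle count condition. From study Cycle 4 the protocol schedules hematology on Day 22 only, and about every 12 weeks from 01 October 2017 (Section 13.10), so some start-of-cycle counts would need a local laboratory.
- Change the Table 7 range from Cycles 2–6 to Cycles 2–12, to match the 12 cycles in Section 16.2.

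Attachment 4 needs no change.
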